#### Exposure categorization for safety studies

For the incidence rate calculations the period of drug use will be divided in mutual exclusive periods of a month to be able to investigate the rate of cardiac events during current, recent or past use. The period 0-180 days after cessation of study drugs use will be classified as recent use and the period 181 days or more will be classified as past use. If patients switch from SR to BP or vice versa, they will contribute to the respective exposure category.

For the case control study we follow the same categorization. A patient will be classified as current user if the last prescription is ongoing or stopped less than 30 days ago before the index date. Patients will be classified as recent users if last prescription stopped between 30 and 180 days before the index date. Patients are past users if the last prescription for a study drug stopped more than 180 days before index date.

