### 9.5.2. Safety study

Bearing in mind that the number of incident users identified in 2012 is of 5,819 patients, we expect that at least 30,000 incident SR users will be included for the period 2004-2012, and a lower number of people (500 to 1,000 per annum) will be eligible for the prospective cohort of incident users as identified in 2013-2015 due to the DHPC, making a total of 31,500 to 33,000 SR users. With the combined prevalence of exclusion criteria described above (29.5% for men and 19.2% for women) (Abrahamsen, 2014) and a 90% participants being of female gender (based on feasibility counts for 2012 in Table (9.5) 1), a minimum of 25,128 incident SR users would be included. Considering a prevalence of SR use of 20% in osteoporotic treated population, around 125,640 incident bisphosphonate users are expected, making a total of over 150,000 study participants.

We assume a conservative annual incidence rate of acute myocardial infarction of 0.19/100 person-years in the general population of participants in EU-ADR databases (Coloma, 2013). Based on this and assuming an average follow-up period after cohort entry of 2 years we would expect 570 cases. Accepting an alpha risk of 0.05, with 90% power, and a prevalence of SR use of 20% amongst controls, **415** MI cases and a 1:10 case-control ratio (**4150** controls) would suffice to recognize as statistically significant an odds ratio greater than or equal to 1.5. Different scenarios of SR use ranging from 10% to 40% and the corresponding number of MI cases required for an  $OR \geq 1.5$  (at fixed alpha 0.05, power 90%) are shown in Figure (9.5.2) 1.

[figure not shown]
**Figure (9.5.2) 1 - Number of MI cases required to ensure 90% power to detect as significant an  $OR \geq 1.5$  for the association between SR use and MI.**

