### 9.7.3.3. Relative risks

Using a matched case control approach we will use conditional logistic regression to estimate the association with the occurrence of endpoints and between current use of SR and 1) past use of study drugs; 2) current use of bisphosphonates. Control for confounding will be based on the change in estimate method as proposed by Greenland *et al* (1993). All analyses will be stratified by period. We will primarily consider factors measured at baseline, and only for those at index date for which we are sure they cannot be an intermediate between drug exposure and outcome.

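### The 90% power in section 9.5.2 belongs to one undivided analysis; the separate comparison from June 2013, part of primary safety objective 2, has roughly 15-30% power for an odds ratio of 1.5

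*Protocol*

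**What the plan says.** Section 9.5.2 makes a single calculation. It takes a "conservative annual incidence rate of acute myocardial infarction of 0.19/100 person-years" and, "assuming an average follow-up period after cohort entry of 2 years we would expect 570 cases". The requirement is put at 415 cases, each with ten controls, on these terms: "Accepting an alpha risk of 0.05, with 90% power, and a prevalence of SR use of 20% amongst controls". According to the section, that number "would suffice to recognize as statistically significant an odds ratio greater than or equal to 1.5". Scenarios with 10% to 40% of controls exposed are mentioned, again for the undivided analysis. For the years after the first safety communication the same section says that "a lower number of people (500 to 1,000 per annum) will be eligible for the prospective cohort".

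The planned analysis is divided. Safety objective 2 in section 8 asks for the SR versus BP comparison both before and from June 2013. Section 9.2.6.2 assigns period by date of cohort entry. Section 9.7.3.3 sets the contrasts as current SR use against past use of study drugs and against current BP use, and adds: "All analyses will be stratified by period". Section 9.3.3 counts a patient as a current user "if the last prescription is ongoing or stopped less than 30 days ago before the index date".

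No case count, exposure prevalence or power is given for either period, or for current use.

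**The concern.** The stated power describes an analysis that puts all starters since 2004 together. One of the two comparisons named in a primary objective rests on a much smaller group. Because period follows cohort entry, person-time after June 2013 from patients who started earlier does not add to the later stratum, which has only its own few starters.

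This study was requested by the regulator after a cardiac signal. If the estimate from June 2013 shows no significant excess, a reader who knows the 90% figure may take that as reassurance that the stratum cannot give.

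**Working it through.** **1. The plan's own figures.** With p0 = 0.20 and OR = 1.5, exposure among cases is p1 = 1.5 × 0.20 / (1 + 0.20 × 0.5) = 0.2727. The two-sided two-proportion formula with 10 controls per case gives 385 cases (weighted pooled variance), 407 (simple-average pooled variance) or 426 (unpooled). At 415 cases, power is 0.92 (weighted pooled) or 0.89 (unpooled). So 415 reproduces. The expected cases reproduce as 150,000 × 2 × 0.0019 = 570.

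**2. Eligible share.** Section 9.5.2 assumes 90% women and exclusions of 19.2% (women) and 29.5% (men): 0.9 × 0.808 + 0.1 × 0.705 = 0.7977. Check: 31,500 × 0.7977 = 25,128, as stated.

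**3. BP users per SR user.** 125,640 / 25,128 = 5, so the SR share of the cohort is 1/6 = 16.7%. Both 16.7% and the stated 20% are used below.

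**4. Stratum from June 2013.**
- SR starters: 3 years × 500 to 1,000 = 1,500 to 3,000.
- Eligible: × 0.7977 = 1,197 to 2,393.
- With BP users: × 6 = about 7,180 to 14,360.
- MI cases: × 2 × 0.0019 = 27.3 to 54.6, against 415 needed.
- MI cases expected among the SR users themselves at that rate: 4.5 to 9.1.

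Power for OR 1.5, pooled formula, 1:10:
- 20% exposed: 16% to 26%
- 16.7% exposed: 16% to 24%
- 10% exposed: 13% to 20%

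The unpooled formula at 20% gives 13% to 21%. The OR detectable with 90% power is about 3.9-4.1 with 27 cases and 2.7-2.8 with 55.

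**5. If BP starts did not fall with SR starts (assumption).** The earlier rate is 30,000 × 0.7977 × 5 / 9 years = 13,295 BP users a year. Over 2.5 to 3 years that is 33,238 to 39,885 users, giving about 131 to 161 cases but only about 3% to 7% exposed. Power is 20% to 29%.

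**6. If mean follow-up is 1 to 4 years instead of 2 (assumption).** The stratum has about 14 to 109 cases, and power at 16.7-20% exposed is about 11% to 44%.

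**7. Stratum up to May 2013.** 30,000 × 0.7977 × 6 × 2 × 0.0019 = 546 cases. Power is 97% at 20% exposed, 95% at 16.7% and 85% at 10%. For all 570 cases the figures are 97%, 96% and 86%. At 10% exposed about 650 cases would be needed.

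**8. Current use.** The protocol gives no persistence figure. If 75%, 50% or 30% of the 570 cases fall in current use of either drug (assumed), 428, 285 or 171 cases remain, and power at 20% exposed is 93%, 80% or 60%.

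**The case against.** The best reply is that section 9.5.2 never attaches 90% power to the later period. It ties the figure to 415 MI cases and discloses the low expected number of new SR users. Section 8 and section 9.7.1 also plan analyses of the overall eligible population, and section 9.7.4 adds a pooled individual-level analysis to gain power. So the calculation matches an analysis that is planned. The checklist in section 14.2 marks that no formal hypothesis is specified, and every eligible patient is included whatever the power. All of this is correct and limits the point to what is claimed for the later stratum. It does not remove it: objective 2 names that comparison, and the only power statement for the safety study does not apply to it.

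Two stronger readings are tempting and are not supported.

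- A reader might infer that the whole study is underpowered because only current users count. The share of current use is not in the documents. The 2-year mean follow-up is itself an assumption, and follow-up in section 9.2.6.2 is not cut off at stopping treatment, so it could be longer. The MI rate is a general-population rate that the protocol calls conservative, while this cohort is aged 50 or older. Past users leave only one of the two contrasts; in the other they are the reference.
- A reader might infer that only the later period shows whether SR is safe in the restricted population. Section 9.2.5.3 excludes contra-indicated patients from the comparison in both periods, and section 9.9 says why. The earlier stratum therefore also informs on patients without contra-indications.

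The later-stratum figures are approximate in both directions. The 2013-2015 count includes January to May 2013, which belongs to the earlier stratum, and it omits later entrants although data waves run into 2017. Section 6 expects few or no new SR users in Italy from April 2014.

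**Conclusion.** The point holds for the stratum from June 2013. On the protocol's own inputs it has about 27-55 MI cases and roughly 15-30% power for an OR of 1.5, with a detectable OR of about 2.7 to 4 at 90% power. This rests on three years of SR starters at the stated 500 to 1,000 a year, the stated exclusions, five BP users per SR user (or stable BP starts), 2 years of follow-up and the pooled formula. Departing from these moves power to between about 11% and 44%, nowhere near 90%.

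The 415 is not an arithmetic error. The all-period and earlier-period analyses keep 90% power or more at 16.7-20% exposure and about 85% at 10%. What limiting the contrast to current use does to them cannot be settled from the protocol and can only be shown as a range.

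**What to change.** In section 9.5.2:

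- Confine the 90% statement to the all-period and pre-June 2013 analyses.
- For each period, state the expected MI cases, the exposure prevalence based on current use at the index date (as a range, since persistence is unknown), and the power or detectable OR.
- Say that the estimate from June 2013 will be reported as an OR with its confidence interval, and that a null result there will not be read as evidence of no increased risk.

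The cost is a paragraph of protocol text and a few power lines, with no change to data or design. The downside is a less favourable stated power.

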### 9.3. Variables

#### 9.3.1. Safety endpoints

**Ascertainment of cases:** cases will be all persons with a first occurrence after cohort entry of:

- Acute myocardial infarction.
- Thromboembolic events (deep venous thrombosis and pulmonary embolism).
- Cardiovascular death.

Cases will be identified from the medical records (see codes in Appendix 14.3).

Acute myocardial infarction has been recently validated in all of the participating data sources (Coloma, 2013; Ramos, 2012) and will therefore not need further linkage or validation studies.

Thromboembolic events have been validated in the UK CPRD/THIN (Lawrenson, 2000) and Aarhus (Severinsen, 2010), and these previously validated algorithms will be used to identify cases. A random sample of cases of thromboembolic events in each data source will be validated using either free text manual review (IPCI, HSD, and Aarhus) or linkage to hospital admissions data (THIN and SIDIAP). If the estimated positive predictive value in these samples is >75%, no further validation will be performed for thromboembolic events. Otherwise, all the events observed in the safety study (i.e. cases) will be individually validated, and only those found to be valid (either by manual review or related hospital admission from hospital records databases, as proposed above) will be defined as cases.

As for cardiovascular death, HSD, IPCI and SIDIAP will combine ICPC and ICD9/ICD10 codes (for hospital admission/primary care records) respectively with mortality using a time specific window to define cardiovascular death. In THIN, data will be linked to the official mortality registry (office for national statistics) for cause of death. In Aarhus, safety endpoints will be identified in the patient registry (hospital discharge and death registry) and no manual validation in the medical records will be done.

**Control selection:** In the nested case control study, each case will be matched by age (same year of birth), index date, gender, and country/data source to 10 controls selected from the cohort using incidence density sampling.

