## Information bias

Information bias may occur to not measuring correctly exposure, outcomes or co-variables.

Regarding exposure, most databases that participate in the study capture prescriptions rather than dispensings. Misclassification of exposure may occur due to lack of ‘picking up’ the prescribed medication and non-compliance. This may overestimate utilization of SR/BP and lead to non-differential misclassification of the comparative studies. Misspecification of the risk window may lead to information bias. The effect of a potential misspecification will be addressed in sensitivity analyses

Lack of recording of certain co-variables (e.g. history of fractures rather than BMD) may lead to misclassification and underestimation of the contra-indications and new indications. Similarly, lack of recording of safety events may lead to misclassification of the safety endpoints. However, previous work has shown very high validity of the coding of myocardial infarction, with positive predictive values ranging from 75% to 100% within EU-ADR Alliance partners (Coloma, 2013). DVT and VTE were only validated in some databases before and will therefore need validation in each of the data sources. Cardiovascular death may be misclassified if no autopsy is done. Validation studies will be conducted in databases where this information is not yet available (See Section 9.3.1).

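### The 415 MI cases in section 9.5.2 are true cases; on the protocol's own PPV range more coded cases are needed, though the expected 570 cover most of the gap

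*Protocol*

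**What the plan says.** Protocol section 9.5.2 sizes the comparative safety study on acute myocardial infarction. The inputs are "Accepting an alpha risk of 0.05, with 90% power, and a prevalence of SR use of 20% amongst controls", and the conclusion is that 415 cases with 4150 controls "would suffice to recognize as statistically significant an odds ratio greater than or equal to 1.5". Figure (9.5.2) 1 extends this to other levels of SR use. The same section derives the case count it anticipates: "assuming an average follow-up period after cohort entry of 2 years we would expect 570 cases".

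Section 9.3.1 says that cases are identified from medical records by the code lists in Appendix 14.3. It adds that MI has recently been validated in all participating sources and "will therefore not need further linkage or validation studies". Section 9.9, under information bias, describes MI coding as highly valid, "with positive predictive values ranging from 75% to 100% within EU-ADR Alliance partners". Neither 9.5.2 nor the title of its figure refers to that range.

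**The concern.** A PPV below 100% means that some coded cases are not MIs. If those cases use SR as often as controls do, they pull exposure among cases towards that of controls, so the odds ratio that the analysis sees is smaller than the true one and more coded cases are needed for the same power. The protocol reports an error range for its case definition and then sizes the study as if the error were zero.

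The stake is how a null result is read. This is a safety study requested by regulators. A non-significant finding backed by a statement of 90% power for an odds ratio of 1.5 would look more reassuring than it is if that power applies only to perfectly classified cases.

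**Working it through.** **Inputs.** From section 9.5.2: alpha 0.05, power 90%, SR use in controls p0 = 0.20, odds ratio 1.5, 10 controls per case, 415 cases required, 570 expected. From section 9.9: PPV 75% to 100%. Not in the protocol, and assumed here:
- The test is two-sided. (One-sided gives 316 to 331 cases, which does not match 415.)
- False-positive cases have the controls' exposure of 20%.
- The expected 570 are coded cases.

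**Reproducing 415.** Exposure in true cases is p1 = 1.5 × 0.20 / (1 + 0.20 × 0.5) = 0.2727, so p1 − p0 = 0.0727.
- Unpooled variance: n = (1.960 + 1.282)² × [p1(1 − p1) + p0(1 − p0)/10] / (p1 − p0)² = 10.507 × 0.2143 / 0.00529 = 426.
- Pooled variance under the null: 385, or 400 with continuity correction.
- Matched formula: 384 with no case-control exposure correlation, 419 with a correlation of 0.2.

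The protocol does not name its formula, but 415 lies within this spread. Power at 415 true cases is 92.0% (pooled) or 89.3% (unpooled). The stated figure is therefore reproduced for correctly classified cases.

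**Adding the PPV.** Exposure in coded cases is pm = PPV × 0.2727 + (1 − PPV) × 0.20. At PPV 75%, pm = 0.2045 + 0.0500 = 0.2545. The odds ratio that the analysis sees is (0.2545/0.7455) / (0.20/0.80) = 1.37.

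Coded cases for 90% power at PPV 75%, unpooled: 10.507 × (0.2545 × 0.7455 + 0.016) / 0.0545² = 727. The pooled formula gives 670, or 690 with continuity correction.

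Results across the range (pooled / unpooled):

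| PPV | Coded cases for 90% power | Power, 415 coded cases | Power, 570 coded cases |
|---|---|---|---|
| 100% | 385 / 426 | 92.0 / 89.3% | 97.5 / 96.3% |
| 95% | 425 / 469 | 89.4 / 86.3% | 96.2 / 94.7% |
| 90% | 471 / 518 | 86.3 / 82.7% | 94.4 / 92.5% |
| 85% | 526 / 576 | 82.6 / 78.6% | 92.1 / 89.7% |
| 80% | 591 / 645 | 78.2 / 74.0% | 89.0 / 86.2% |
| 75% | 670 / 727 | 73.2 / 68.8% | 85.1 / 81.9% |

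With 570 coded cases, power reaches 90% at a PPV of 81.5% (pooled) or 85.4% (unpooled). With 415 coded cases, the pooled formula needs a PPV of 96.1%; the unpooled formula gives slightly under 90% even at 100%.

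**The case against.** Several points on the other side are sound.

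- **No number is wrong.** Section 9.5.2 speaks of MI cases, and 415 is right for those. What is missing is a qualification.
- **The study does not stop at 415.** Section 9.5 includes all eligible participants, and 570 cases are expected. A reader might infer from the 415 column that the study has only about 70% power. The protocol does not support that: 415 is a minimum, and at the expected count the worst case is 82-85%.
- **MI coding is not unvalidated.** A reader might infer this from the decision to do no more validation. Section 9.3.1 relies on earlier validation in all sources and declines only further work.
- **The pooled PPV is unknown.** The range in 9.9 runs across partners. The 75% end applies only if the pooled PPV sits at the floor. SIDIAP supplies 4008 of the 5819 incident SR users counted for 2012 (69%), and the protocol gives no PPV for it.
- **The dilution may be smaller.** If some false positives are other ischaemic events that SR also affects, less is lost. For illustration, an odds ratio of 1.25 among false positives gives 92-94% power with 570 cases at PPV 75%.
- **The rate may count true MIs.** The protocol does not say whether 0.19 per 100 person-years is a coded or a confirmed rate. If 570 were true MIs, the coded count at PPV 75% would be 570 / 0.75 = 760, above the 670 to 727 needed.
- **Misclassification is acknowledged.** Section 9.9 discusses it, and for thromboembolic events 9.3.1 accepts a PPV above 75% as adequate.

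These points limit the size of the problem and rule out calling it an arithmetic error. They do not remove it: the stated requirement is not tied to true cases, and the PPV that the protocol itself reports never reaches the study size.

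**Conclusion.** The point holds in a limited form. The figure of 415 is correct for true MI cases and does not carry over to coded cases unless the PPV is close to 100%. At the bottom of the protocol's own range, about 670 to 727 coded cases are needed, more than the 570 expected.

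At 570 coded cases the loss is modest. Power stays at about 90% or more down to a pooled PPV of about 82-85%, and at 75% it falls 5 to 8 percentage points short of the target. This rests on a two-sided test, on false positives exposed like controls, and on the 570 being coded cases. The range within each figure reflects the choice of formula, which the protocol does not state.

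**What to change.** In section 9.5.2 and Figure (9.5.2) 1:

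1. Label 415 as true (correctly classified) MI cases.
2. State the assumed SR exposure of false-positive cases, and whether the 570 counts coded or confirmed events.
3. Add the coded cases needed for 90% power, and the power at the expected case count, across PPV 75% to 100%, naming the formula used.
4. Claim 90% power for an odds ratio of 1.5 at 570 coded cases only for a pooled PPV of about 85% or higher.

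The cost is a short addition to the text and one recomputed figure. Data collection and analysis do not change. The downside is that the stated power becomes slightly less favourable.

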### 9.6. Data management

The EU-ADR Alliance works in a federated manner: data extraction and elaboration is done locally and pooling of aggregated data is done on a remote research environment (see Figure (9.6) 1 for overview).

**Figure (9.6) 1 - Model for data sharing and elaboration**

Due to the different database characteristics and coding schemes it is not possible to use one single data extraction algorithm for all the databases. To reconcile differences across terminologies a shared semantic foundation will be built for the definition of events under study by selecting disease concepts from the Unified Medical Language System (UMLS, V.2008AA), and set up a multi-step and iterative process for the harmonization of event data. The sequential steps of this process are shortly described below:

All events/outcomes and (contra)-indications will be ascertained using a list of agreed ICD (Denmark, Italy, and Spain), ICPC (Netherlands) and READ (UK) codes. The proposed lists of codes (See Appendix 14.3.2) were created following a number of steps:

1. Clinical definition;
2. Preliminary list of concept identifiers using UMLS Metathesaurus Browser;
3. Addition of codes found after literature review of validated lists of codes for each of the study outcomes in each of the databases; and
4. Consensus with academic partners involved in the management and analysis of each of the data sources. As coding might change over time, relevant codes might be updated during the course of the project. Harmonization of these code lists will take place between databases by comparison of population based age and sex specific incidence rates, according to standard quality assurance procedures in the EU-ADR Alliance (see below).

The sets of codes proposed in Appendix 14.3.2 will be further discussed with each of the academic partners during the first months of the study, and before data extraction.

### 9.6.1. Identification of Unified Medical Language System® (UMLS®) concepts

A UMLS concept is identified by a Concept Unique Identifier (CUI) and describes a single medical notion that can be expressed using different synonyms (terms). For each event, a medical definition will be created and, based on such definition relevant UMLS concepts are identified and projected into the database-specific terminologies. In addition, for those databases where free text is available, the labels of the codes are considered for free text search of the events.

